3.2 Exclusion Criteria

- 3.2.1 Autoimmune disease requiring treatment within the last 5 years including systemic lupus erythematosus, rheumatoid arthritis, multiple sclerosis, Sjögren's syndrome, autoimmune thrombocytopenia, uveitis, or other if clinically significant
- 3.2.2 Major surgery or a wound that has not fully healed within 4 weeks of enrollment.
- 3.2.3 History of stroke or intracranial hemorrhage within 6 months prior to enrollment.
- 3.2.4 Requires anticoagulation with warfarin or equivalent vitamin K antagonists.
- 3.2.5 Requires chronic treatment with strong CYP3A inhibitors.
- 3.2.6 Vaccinated with live, attenuated vaccines within 4 weeks of enrollment.
- 3.2.7 Known history of human immunodeficiency virus (HIV) or active Hepatitis C Virus or active Hepatitis B Virus infection or any uncontrolled active systemic infection.
- 3.2.8 Known CNS lymphoma.
- 3.2.9 Subjects with a history of prior malignancy with the exception of non-melanoma skin cancer, carcinoma in situ of the cervix, in situ carcinoma of the bladder, stage 1 prostate cancer that does not require treatment, or other malignancy that has undergone potentially curative therapy with no evidence of disease for the last > 2 years and that is deemed by the investigator to be a low risk for recurrence.

- 3.2.10 History of allergic reactions attributed to compounds of similar composition to SD-101 or ibrutinib
- 3.2.11 Treatment with an immunosuppressive regimen of corticosteroids or other immunosuppressive medication (eg, methotrexate, rapamycin) within 30 days of study treatment. Note: subjects may take up to 5 mg of prednisone or equivalent daily. Topical and inhaled corticosteroids in standard doses are allowed.
- 3.2.12 Significant cardiovascular disease (ie, NYHA class 3 congestive heart failure; myocardial infarction with the past 6 months; unstable angina; coronary angioplasty with the past 6 months; uncontrolled atrial or ventricular cardiac arrhythmias).
- 3.2.13 Pregnant or breast feeding.
- 3.2.14 Any other medical history, including laboratory results, deemed by the investigator to be likely to interfere with their participation in the study, or to interfere with the interpretation of the results.

3.3 Informed Consent Process

All participants must be provided a consent form describing the study with sufficient information for participants to make an informed decision regarding their participation. Participants must sign the IRB approved informed consent prior to participation in any study-specific procedure. The participant must receive a copy of the signed and dated consent document. The original signed copy of the consent document must be retained in the medical record or research file.

3.4 Randomization Procedures

This is a non-randomized trial.

3.5 Study Timeline

Primary Completion:

The study will reach primary completion 60 months from the time the study opens to accrual.

Study Completion:

The study will reach study completion 60 months from the time the study opens to accrual.

4. TREATMENT PLAN

4.1 Dose de-escalation Study Design

The study will use a 6+3 design with a goal of determining the recommended phase 2 dose. We will enroll a cohort of 6 subjects, with a 3 mg dose of intratumoral SD-101 and 560 mg dose of oral ibrutinib. The proposed initial dose of SD-101 is below the maximum tolerated dose as determined in previous trials, and there is extensive data regarding the safety of treatment with ibrutinib at the FDA-approved dose of 560 mg. Because no additional toxicity is anticipated with combination therapy of SD-101 and ibrutinib, the 6+3 dose de-escalation design will be employed, permitting rapid confirmation of the safety of the combination therapy and selection of the recommended phase 2 dose while still allowing detection of any unanticipated toxicity.

If 0 or 1 subjects out of the initial 6 subjects experience a DLT, we will chose this dosing as the recommended phase 2 dose level. If 2 out of 6 subjects experience a DLT, we will expand the

cohort and enroll an additional 3 subjects at the same dose level. If 3 out of 6-9 subjects in the initial dose cohort experience a DLT, then the dose de-escalation cohort -1 will accrue. This dose de-escalation cohort will be treated with 1 mg intratumoral SD-101 and 560 mg ibrutinib. If \leq 2 out of 6 subjects in the dose de-escalation cohort experience a DLT, then this dose will be considered the RP2D. If 3 or more subjects in the de-escalation cohort experience a DLT, the study will be stopped.

Table 1. Dose Escalation Plan

Cohort	Dose (mg)	Total Enrollment per Cohort	Dose Escalation Rules
-1	1 mg SD-101 560 mg ibrutinib	6	1 of 6 or 2 of 6 DLT, RP2D is established 3 of 6 DLT, trial is stopped
1	3 mg SD-101 560 mg ibrutinib	6-9	0 of 6 or 1 of 6 DLT, RP2D is established at this level 2 of 6 DLT, expand cohort to 9 subjects 2 of 9 DLT, RP2D is established at this level 3 of 6-9 DLT, decrease to dose level -1
Phase 2 Expansion	RP2D	15	If the incidence of study drug-related DLTs as defined previously equals or exceeds 33% of treated subjects at RP2D dose level 1, enrollment will be stopped for dose level 1, and enrollment of 15 subjects will begin at dose level -1. If the incidence of study drug-related DLTs equals or exceeds 33% of treated subjects at RP2D dose level -1, then the trial is stopped

Phase 2 (SD-101 dose Cohort Expansion): Once the safety profile and tolerability of all doses tested has been characterized and the RP2D of SD-101 has been defined during the dose de-escalation phase of this trial, the RP2D dose cohort will be expanded by an additional 15 subjects. This will enable further characterization of the immunoregulatory activity and preliminary antitumor effects of this treatment regimen. The treatment schema for SD-101, RT and ibrutinib will remain the same as previously described.

Clinical safety monitoring of subjects enrolled during this additional Cohort Expansion portion of the study will be the same as conducted during the dose escalation portion of the study (ie, part 1). If the chosen RP2D is dose level 1 (3 mg SD-101) and the combined incidence of study drug-related DLTs of any kind (ie, Grade 3 injection site reaction, hematologic or non-hematologic DLT) is equal to or exceeds 33% of treated subjects at any point during treatment, this will prompt a halt in enrollment at that dose level. Enrollment of 15 subjects will then begin at the lower dose level of 1 mg SD-101. If the incidence of DLTs in the lower dose cohort equals or exceeds 33%, the trial will be stopped.

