10.1.3 Measurement Time Points

Dose-limiting toxicity will be assessed continuously throughout the trial. Adverse event information will be collected at each visit. Safety labs will be collected on Days 9; 23; 37; week 12; and every 12 weeks thereafter until the final study visit.

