10.2.1 Relevant Subset

This outcome will be measured on any individual who has received at least one intratumoral injection of SD-101 at the recommended phase 2 dose level. This will include any subjects treated during the phase 1B portion who were treated at the recommended phase 2 dose level.

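### The 33% DLT limit in 4.1 does not say whether phase 1b subjects count and sets no minimum number treated, and that choice can decide whether a dose is dropped or the trial stops

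*Combined protocol and SAP*

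**What the plan says.** Section 4.1 sets two kinds of DLT rule.

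- **Phase 1b.** At 3 mg the dose is accepted with 0/6, 1/6 or 2/9 DLTs. If 3 mg fails, six subjects are treated at 1 mg. When at most 2 "out of 6 subjects in the dose de-escalation cohort experience a DLT, then this dose will be considered the RP2D"; the cohort -1 row of Table 1 agrees: "1 of 6 or 2 of 6 DLT, RP2D is established". Three or more DLTs stop the study.
- **Phase 2 expansion (15 subjects).** At 3 mg, enrolment halts if DLT incidence "is equal to or exceeds 33% of treated subjects at any point during treatment". Then, "Enrollment of 15 subjects will then begin at the lower dose level of 1 mg SD-101". For that dose the text says: "If the incidence of DLTs in the lower dose cohort equals or exceeds 33%, the trial will be stopped". The expansion row of Table 1 gives the 1 mg limit as: "If the incidence of study drug-related DLTs equals or exceeds 33% of treated subjects at RP2D dose level -1, then the trial is stopped".

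Section 10.1.3 adds: "Dose-limiting toxicity will be assessed continuously throughout the trial". Section 10.1.1 counts DLTs up to Day 731.

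For the response endpoint, section 10.2.1 settles who is counted: "This will include any subjects treated during the phase 1B portion who were treated at the recommended phase 2 dose level". The 33% rule has no such sentence. In the 3 mg rule the incidence is described as combined, but the parenthesis after it lists kinds of DLT, not study phases. The safety population in 12.2.1 is an analysis set and is not tied to this rule.

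**The concern.** A percentage limit needs a denominator and a first point of application. This rule has neither, and each natural way of supplying the denominator causes trouble.

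- **Phase 1b counted.** The 1 mg result that opens the expansion, 2/6, is also one that stops the trial.
- **Expansion only.** With no minimum number, a single early DLT can reach 33%.

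The rule decides whether 3 mg is abandoned and whether the trial ends. In an open-label, single-centre study, the denominator should not be left to be settled after the DLTs are known.

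**Working it through.** **Inputs.** From 4.1: a limit of at least 33%, 15 expansion subjects, and the phase 1b acceptance rules above. The documents give no DLT rate, so 10%, 20% and 1/3 are assumed (up to 40% at 3 mg in step 2). The plan states no stopping probability for this rule, so there is no figure of its own to reproduce.

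**1. Overlap if phase 1b counts.** At 1 mg, 2/6 = 33.3%, which is at least 33%. At 3 mg every accepted result is below the limit: 0/6 = 0%, 1/6 = 16.7%, 2/9 = 22.2%. The clash is therefore specific to 1 mg.

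**2. How often the 1 mg clash could arise.** 3 mg must fail in phase 1b, and 1 mg must then give exactly 2/6. With DLT rate p at 3 mg and q at 1 mg:

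P(3 mg fails) = 1 − [P(X ≤ 1 of 6) + P(X = 2 of 6)(1 − p)³]; P(2/6 at 1 mg) = 15q²(1 − q)⁴.

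| p at 3 mg | q at 1 mg | P(3 mg fails) | P(2/6 at 1 mg) | Product |
|---|---|---|---|---|
| 20% | 10% | 0.219 | 0.098 | 0.022 |
| 1/3 | 20% | 0.551 | 0.246 | 0.136 |
| 40% | 1/3 | 0.700 | 0.329 | 0.230 |

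**3. Opposite decisions at 3 mg.** Suppose 3 mg is accepted at 1/6 and one of the first three expansion subjects has a DLT. Expansion only, checked when that DLT occurs: 1/1, 1/2 or 1/3, so enrolment halts. Phase 1b counted: 2/7 = 28.6%, 2/8 = 25.0% or 2/9 = 22.2%, so it continues. The chance of at least one DLT in three subjects is 1 − (1 − p)³ = 27%, 49% and 70% at 10%, 20% and 1/3.

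**4. Chance of meeting the limit over 15 expansion subjects.** Subjects are added one at a time, each with DLT probability p. A path ends when DLTs divided by number treated first reaches 0.33 at a permitted check.

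| Count and timing | 10% | 20% | 1/3 |
|---|---|---|---|
| Expansion only, from subject 1 | 0.2995 | 0.5831 | 0.8571 |
| Expansion only, from subject 6 | 0.1291 | 0.4203 | 0.7865 |
| Expansion only, at subject 15 only | 0.0127 | 0.1642 | 0.5959 |
| 3 mg, phase 1b counted, starting at 0/6 | 0.0028 | 0.0437 | 0.2794 |
| 3 mg, phase 1b counted, starting at 1/6 or 2/9 | 0.0395 | 0.1950 | 0.5584 |
| 3 mg, phase 1b counted, weighted | 0.0191 | 0.1442 | 0.5038 |

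The last row weights the accepted phase 1b results 0/6, 1/6 and 2/9 by their relative probabilities: 0.555/0.370/0.075, 0.336/0.503/0.161 and 0.196/0.587/0.217. At 10%, for example, 0.555 × 0.0028 + 0.445 × 0.0395 = 0.0191.

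**5. After 2/6 at 1 mg, phase 1b counted.** As written, the limit is already met, so the trial stops with certainty. With a limit of more than one-third, 2/6 continues, 3/7 (42.9%) stops, and the chance of stopping over 15 further subjects is 0.2216, 0.4789 and 0.7857. If the 33% limit were kept but the check at 2/6 skipped, so that checking began at the next subject, the figures would be 0.2995, 0.5831 and 0.8571.

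**Timing assumption.** Each DLT outcome is taken as known before the next subject enters. At the planned 10 subjects a year (365/10 = 36.5 days apart) this is roughly right for Day 1–30 DLTs. Later DLTs, including any in phase 1b subjects during the expansion, are not modelled.

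**The case against.** The best defence is sequence. The 33% rule appears only in the expansion row of Table 1 and in the phase 2 text of 4.1, while cohort -1 has its own rule. The phrase about the lower dose cohort directly follows the opening of 15 places at 1 mg. Read that way, phase 1b chooses the dose, the 33% limit governs the expansion alone, and 2/6 causes no conflict. This is a fair reading and may be the intended one. It is not stated, though, and Table 1's reference to treated subjects at the dose level can equally include phase 1b.

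The clash is also remote: the larger figures in step 2 need 3 mg DLT rates of 1/3 or 40%. Section 4.1 anticipates no added toxicity, and section 5.1 reports no DLT in the completed 1, 2 and 4 mg cohorts of SD-101 with radiation. Those cohorts had no ibrutinib, so this is only partial reassurance.

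Checking from subject 1 is an inference. "is equal to or exceeds 33% of treated subjects at any point during treatment" may describe when in a subject's treatment a DLT occurs, and it stands only in the 3 mg rule. "Dose-limiting toxicity will be assessed continuously throughout the trial" describes assessing DLTs, not applying the limit. If the limit were tested only at subject 15, the chances fall to 1%, 16% and 60%. This objection stands as to size. It also shows that the result depends on timing the plan does not fix.

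Finally, reaching the limit at 3 mg moves enrolment to 1 mg and does not end the trial, and the DSMC regularly reviews serious adverse events (11.2). Neither supplies the missing denominator.

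**Conclusion.** The point holds and should be fixed: the 33% limit has no stated denominator and no minimum number treated. At an assumed 10% DLT rate, the chance of halting 3 mg is about 2% with phase 1b counted and 30% with expansion subjects only checked from subject 1. At 20% it is 14% against 58%, and at 1/3 it is 50% against 86%.

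A reader might infer two stronger conclusions that the documents do not support. One is that 4.1 flatly contradicts itself at 1 mg. It does so only if phase 1b subjects count, and even then the result arises in about 2% to 23% of trials under the assumed rates. The other is that one early expansion DLT must halt the dose. That needs both an expansion-only count and checking as subjects accrue, and the text suggests such checking without stating it.

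All probabilities rest on assumed DLT rates and on the timing assumption in the working. The arithmetic at 2/6 and the opposite decisions in step 3 do not depend on the rates.

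**What to change.** In 4.1 (phase 2 paragraph and Table 1), state that:

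- the rule counts all subjects treated at that dose level, phase 1b included;
- it is first applied once at least 6 have been treated at that dose, with an immediate stop at that dose if 3 DLTs occur sooner;
- the limit at 1 mg is more than one-third, so that 2/6 can open the expansion, while 3 mg keeps 33%;
- a subject enters the denominator at a named time, for example Day 30 or at a DLT if earlier, because DLTs run to Day 731.

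The early stop matters where 1 mg opens after 3 mg is halted in the expansion, with no phase 1b subjects at 1 mg. Three or more DLTs in the first five have probability 0.9%, 5.8% and 21% at 10%, 20% and 1/3. It matches the phase 1b rule and leaves the overall stopping chances unchanged, since 3 DLTs by subject 5 give at least 3/6 at subject 6.

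Equally acceptable, with the 33% limit unchanged: state that only expansion subjects count, first checked at subject 6, with the same early stop at 3 DLTs and a stated time of entry to the denominator. The chances are then 13%, 42% and 79%.

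**Cost.** Wording only, with no change in sample size. The preferred version gives a somewhat looser limit:

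- After 2/6 at 1 mg, the chance of stopping is 22%, 48% and 79%, against certainty under the pooled 33% rule as written.
- Where 1 mg opens with no phase 1b subjects, it is 4%, 25% and 66%, against 30%, 58% and 86% at 33% checked from subject 1.
- At 3 mg with a true rate of 1/3, counting phase 1b gives a 50% chance of a halt, against 86% for expansion only from subject 1.
- A 3/9 result would continue at 1 mg although it de-escalates at 3 mg.

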4.2 Informed Consent and Screening Period

Subjects who may be eligible for the trial will be approached by the Investigator and offered participation in the trial. The Investigator or co-Investigator will explain the study to the potential subject verbally, providing all pertinent information (purpose, procedures, risks, benefits, alternatives to participation, etc.), and will allow the potential subject ample opportunity to ask questions. Following this verbal explanation, the potential subject will be provided with the IRB approved informed consent form and will be afforded sufficient time to consider whether or not to participate in the research. After allowing the potential subject time to read the consent form, the investigator or approved designee (study coordinator) will answer any additional questions the potential subject may have and will obtain the subject's signature on the consent form. The investigator or designee will also sign the consent form. A signed copy of the consent form will be given to the subject, scanned into the medical record and distributed to the pharmacy and CTRU as per Stanford Cancer Clinical Trials Office (CCTO) Standard Operating Procedures. Before any protocol-specified procedures are conducted, each prospective participant must provide informed consent.

The screening period will take place up to 4 weeks prior to first dosing. Studies to evaluate the extent of tumor burden may be performed up to 6 weeks prior to dosing.

Subjects will undergo the following procedures during the screening period:

- Written informed consent
- Medical history and complete physical exam
- Obtain vital signs / ECOG performance status
- Monitoring of concomitant medications
- Hematology: CBC, differential, platelet count
- Chemistry: comprehensive metabolic panel
- LDH
- Urine pregnancy test (for females of childbearing potential)
- Determination of extent of disease with CT scans or PET/CT to evaluate all areas of known or suspected neoplastic disease. Procedures performed prior to subject entry into the trial, but within 6 weeks of first dosing, will fulfill the screening requirements.
- Infectious disease screening- HIV antibody testing, Hepatitis B surface antigen, Hepatitis B core antibody and Hepatitis C antibody testing
- Fine needle aspiration of planned treatment site (if no tissue from excisional biopsy is available for correlative studies). If additional sites of disease are safely accessible via fine needle aspiration, these may be biopsied as well.
- An excisional biopsy may be performed to confirm that the tumor has not transformed to a more aggressive form (optional). Tissue/cells not required for clinical diagnostic assessment may be collected and stored for immune correlative studies.
- Collection of 1 purple top tube for research correlates
- *Only for subjects with sufficient material from an excisional biopsy or, optionally, for patients with circulating lymphoma cells:* Apheresis for collection of peripheral blood

mononuclear cells (PBMC) (approximately 2 hours) to provide adequate sample for immune assays

- *Only for subjects not undergoing apheresis:* 7 additional green top tubes of peripheral blood will be collected for research correlates

4.3 Treatment Period:

The treatment schema and study visit schedule is the same for both the dose de-escalation cohorts and the expanded, phase 2 cohort.

SD-101 will be administered within 12 hours of the completion of radiotherapy during Day 2.

The study agent SD-101 at a dose of either 1 mg or 3 mg will be injected intratumorally on Day 2. Subsequent weekly injections will be administered on days 9, 16, 23 and 30 for a total of 5 intratumoral injections.

Ibrutinib will be taken PO daily starting on Day 10. Dosing will be continuous 560 mg daily throughout the course of the trial. Subjects will continue to take ibrutinib until disease progression or for a total of 96 weeks of therapy, whichever comes first.

All intratumoral SD-101 injections will be carried out at the Clinical Translational Research Unit (CTR) and/or oncology clinic infusion treatment area (ITA). Vital signs, including weight, will be taken prior to each injection. Subjects will be monitored for at least 30 minutes after each injection with repeat vital signs before being discharged home. Vital signs (blood pressure, heart rate, temperature, respiratory rate and oxygen saturation via pulse oximetry) should be obtained at the end of the monitoring period, within a -5/+15 minute window.

All subjects will be evaluated as described below. The first day of treatment is Day 1, which is the first day of Week 1. Subsequent days or weeks listed are with reference to his landmark.

4.3.1 Day 1:

- First treatment of radiotherapy (2 Gy)

4.3.2 Day 2:

- Obtain vital signs/ ECOG performance status
- Assessment of adverse events and toxicity grading according the CTCAE v4.0
- Monitoring of concomitant medications
- Second treatment of radiotherapy (2 Gy)
- Administration of intratumoral injection no. 1 of SD-101 within 12 hours of radiotherapy

4.3.3 Day 4 (+/- 1 day):

- *Optional* (encouraged but not mandatory) FNA of accessible tumor for research studies. If additional (untreated) sites of disease are safely accessible via fine needle aspiration, these may be biopsied as well.

4.3.4 Day 9 (+/- 2 days)

- Obtain vital signs/ ECOG performance status
- Assessment of adverse events and toxicity grading according the CTCAE v4.0
- Monitoring of concomitant medications
- CBC with Differential and platelet count
- Comprehensive Metabolic panel
- FNA of accessible tumor for research studies. To be performed prior to intratumoral injection no. 2. If additional (untreated) sites of disease are safely accessible via fine needle aspiration, these may be biopsied as well.
- Collection of 1 purple top tube for research correlates. Collection should occur before SD-101 injection no. 2.
- Administration of SD-101 intratumoral injection no. 2 at the same site as previously
- Collection of 7 peripheral blood green top tubes for research correlates
- Distribution of 1 month supply of ibrutinib. Administration of first dose of ibrutinib 560 mg orally will occur the next day. Ibrutinib will be self-administered by the subject daily from this point until progression of disease or for 96 weeks, whichever comes first.

4.3.5 Day 16 (+/- 2 days)

- Obtain vital signs/ ECOG performance status
- Assessment of adverse events and toxicity grading according the CTCAE v4.0
- Monitoring of concomitant medications
- Collection of 7 green top tubes for research correlates
- Administration of SD-101 intratumoral injection no. 3

4.3.6 Day 23 (+/- 2 days); Day 30 (+/- 2 days)

- Obtain vital signs/ ECOG performance status
- Assessment of adverse events and toxicity grading according the CTCAE v4.0
- Monitoring of concomitant medications
- CBC with Differential and platelet count at Day 23 visit
- Comprehensive Metabolic panel at Day 23 visit
- Administration of SD-101 intratumoral injection no. 4 (Day 23), no. 5 (Day 30) at the same injection site as previously
- Collection of 1 purple top tube for research correlates (Day 23 visit only)

